Appendix A Measures

Characterization

Social Communication Questionnaire (Lifetime) (SCQ) This 40-item survey evaluates communication skills and social functioning in children who may have autism spectrum disorder. The *Lifetime Form* focuses on the child's entire developmental history, providing a Total Score that can be compared to normative data using specific cutoff points. It shows high agreement with the much longer interview called the Autism Diagnostic Interview – Revised. The SCQ can be completed by the parent or other primary caregiver in 10-15 minutes.

Intellectual Functioning Children with ASD range from severely retarded to above average IQ. We will use one of two tests: the Abbreviated Stanford-Binet V, or the Mullen (for low functioning children). The examiner will attempt to complete the Abbreviated Stanford-Binet V. If the child is unable to complete the Abbreviated Stanford-Binet V, the examiner will administer the Mullen.

Vineland Adaptive Behavior Scales (Vineland III) (Interview) assess adaptive functioning across several domains including Socialization, Communication, Daily Living Skills, and an Adaptive Behavior Composite scale, which is derived from the other three scales. The Vineland II relies on an informant (mother or primary caretaker) to provide information about the child's adaptive behavior – i.e., what the child actually *does* in the course of daily living.

Clinical Global Impression - Severity (CGI-S) This is a 7-item scale ranging from a score of 1 for "Normal" to 7 for "Extreme." In the RUPP Autism Network, we have developed a high degree of reliability with the CGI-S. Although SIB will be given particular weight in this study, independent evaluators will consider all aspects of the child's condition to assign the CGI-S score.

Adverse Events Review This 34-item form was developed by the RUPP Autism Network to assist with the elicitation and assessment of adverse effects. The treating clinician will ask specific queries about major body systems, activity level, sleep, appetite, and general health. The Adverse Events Review will be conducted at baseline so that current health complaints are known and documented. New events, whether presumed related to treatment or not, are classified as an adverse event and rated as Mild, Moderate or Severe (See Appendix B for definitions).

Outcome Measures

Direct Observation (described in the body of the protocol)

Aberrant Behavior Checklist (ABC) (described in the body of the protocol)

Clinical Global Impressions-Improvement Scale (CGI-I) (described in the body of the protocol)

Parent Target Problems (PTP) (described in the body of the protocol)

The Diagnostic and Statistical Manual of Mental Disorders, Fifth Edition checklist (DSM-V checklist) lists the criteria for ASD that are outlined in the DSM. The interviewer will go through the checklist and ask the caregiver if each of the symptoms is present in the child and will mark the form accordingly.

Children's Yale-Brown Obsessive-Compulsive Scales-PDD (CYBOCS-ASD) The CYBOCS-ASD is a modified version of the CYBOCS developed for use in children with Obsessive-Compulsive Disorder ([name] et al., 1997). The modified version is a semi-structured clinician-rated scale designed to rate the current severity of repetitive behavior in children with ASD (i.e., Time Spent, Interference, Distress, Resistance, and Control. Each item is scored from 0 (least symptomatic) to 4 (most symptomatic), yielding a Total score from 0 to 20. It has established reliability and validity ([name] et al., 2006) and is sensitive to change ([name] et al., 2014).

Caregiver Strain Questionnaire (CGSQ; Brannan, A.M., Heflinger, C., & Bickman, L, 1997) measures the impact of having a child with a ASD on the family. The questionnaire includes 21 items that assess three dimensions of caregiver strain: objective strain, internalized subjective strain, and externalized subjective strain. Each item is rated on a 5-point scale ranging from 1(not at all a problem) to 5 (very much a problem).

Parent Satisfaction Rating This will be developed for this study. Specific questions will be asked about parents assessment on the usefulness of specific techniques (e.g., the interview used to estimate the function of the behavior, the functional analysis, the use of placebo control). Parents will also be asked whether they would recommend the study to other parents and children with ASD and SIB.

Appendix B

HUMAN SUBJECTS

These inclusion and exclusion criteria described above will guide decisions on study entry.

Sources of Materials

The sources of the research material will be data collected in the course of the clinical trial to determine the efficacy and also to ensure the safety of study participants. The principal types of data will be clinical rating scales and standardized tests (e.g., IQ test). Vital signs and routine laboratory measures (blood chemistry, blood cell counts) and research blood sample will also be obtained.

Potential Risks

The risks associated with these procedures include exposure to the study drug or placebo, and the risk associated with venipuncture. The blood draws poses a possible risk of bruising at the site of the draw, light-headedness and fainting along with a remote chance of infection.

The safety record of NAC is excellent. When used as a dietary supplement, the dose of NAC ranges from 600 to 1000 mg/day. At the other extreme, NAC is given at very high loading doses (140 – 150 mg/kg in the first hour) by infusion in the treatment of acetaminophen overdose (Sandilands and Bateman, 2008). Although rare, anaphylactoid reactions consisting of angioedema, bronchospasm, tachycardia, flushing and hypotension have been reported with IV treatment. Zheng et al. (2014) used 600 mg of NAC twice a day in their 1 year study on the rate of COPD exacerbations compared to placebo. The study included 482 adults in the NAC and 482 adults in the placebo. The rate of serious adverse events (mostly consisting of COPD worsening) was nearly identical in the two groups. Other AEs included abdominal pain (2%), diarrhea (1%) and pruritus (1%).

Although highly unlikely, there are potential privacy risks associated with participating in such a study. There is minimal risk associated with the completion of rating scales and assessment measures.

Protection from Risks & Discomforts Blood draws are common procedures and will be performed by a certified phlebotomist. We will offer a numbing cream prior to the blood drawing procedure. We will systematically review adverse events at clinic visits and will be available by telephone. Parents will be given phone numbers of the principal investigator and study physician – who will be available after hours. The PI and study physician have access to the pharmacy after hours – if it is necessary to break the blind.

The proposed dose of NAC in this study is higher than when it is used as a dietary supplement. But it has been used safely in children and adults in this dose range (Hardan et al., 2012).

Confidentiality will be maintained throughout the project period. With the exception of tests that require date of birth, research records will not include names or contact information. Subjects will be identified only by their code numbers. A file with personal health information (e.g., names and addresses) will be kept separately in a locked file cabinet.

Blood Drawing & Vital signs Protocol: Children with ASD, especially those who engage in challenging behaviors such as self-injury, are at higher risk of having problems with medical procedures such as blood tests. To assist with the safety and success of the blood drawing procedure, we will follow these steps.

- At the initial screen appointment, we will discuss the blood drawing and blood pressure collection procedures with the caregiver and gather information about how these procedures are usually done with the child.
- If the caregiver has a history of successfully completing these procedures with the child, we will encourage the caregiver to follow the same strategies that have worked in the past. Caregivers will also be encouraged to stop

the procedure if they feel their child is demonstrating greater resistance or distress than has occurred in similar situations, or if they feel uncomfortable with the level of the child's distress.

- If the caregiver reports a history of unsuccessfully completing these procedures, we will review the options below to confirm the caregiver's approval. Note: these approaches will have been discussed in the consent process, but will be reviewed again in advance of the actual procedures.
 - Research staff will assist the caregiver in getting the child to the location for the procedure (i.e., nurses office or behavioral session room for vitals and an exam room at the Emory Children's Pediatric Center for the blood draw). This will be done by offering preferred items to the child in the location. A guided transition procedure will be used if necessary (described below).
 - The child will be allowed to remain in the area where the procedure will be conducted with highly preferred items (e.g., toys, iPad) until the caregiver reports that the child is calm enough to attempt the procedure.
 - The clinician will attempt the procedure twice. If the child is resistant and the blood draw cannot be completed, the research staff will use physical guidance to keep the child safe while the clinician attempts the procedure up to two more times.
 - If the procedure is not successful after the above procedures, we will stop attempting and document that the procedure as unsuccessful due to noncompliance.
 - The caregiver will be present for all of these steps. As note, the caregiver will be allowed to stop the process in response to heightened distress level for the child (e.g., the child's distress is greater than exhibited in similar situations).
- If the blood draw or other vitals are not collected due to noncompliance, the research team (including study medical personnel) will meet and review all available information, including past information from the medical record if available through our HIPPA waiver. Based on this information, the team will make a decision about the child's eligibility for the study. The team conference may also include consultation with the child's primary care provider.

Transition procedure involves 1-2 staff members physically guiding the child from one location to another (or keeping the child in a specific safe location). This procedure is approved by the personal protective procedures program used in this patient population at the Marcus Autism Center. All staff members that use the personal protective procedures have undergone a 2-day training and passed both a written and a role-play examination to confirm they are capable of implementing the procedure safely.

Recruitment

All recruitment materials such as flyers, letters and social media posts will be IRB approved. Announcements will be placed on the Marcus website. We will send notices to primary care clinics, local parent organizations, and schools. We will also contact children and families on the Severe Behavior Clinic waiting list at Marcus.

Cost

There will be no costs for study visits of the study medication. The study medication and the matching placebo will be supplied by the BioAdvantex company.

Compensation

There will not be any compensation for study participation.

Consent Process

Interested families will be screened on the telephone by the study coordinator. Presumably eligible and willing families will be invited to Marcus for a formal screening visit. Parental consent will be obtained at the screening visit prior to the collection of any study data. The consent procedure will include the following: (a) provide the consent forms to parents and guardians together with a verbal summary of the contents of all paragraphs, and (b) a description of alternatives to participating in the study (not to take part, use of other treatments, and obtaining similar treatment through other

clinical services). Parents (guardians) will also be told that declining participation will not prejudice their right to pursue other treatments at Marcus, Children's Hospital or Emory.

Parental consent will be obtained by trained investigators as documented on the delegation of authority log. Children whose parents indicate notable barriers to meeting the demands of the study or whose parents lack capacity to understand the purpose and expectations of the study will not be randomized in the study. These judgments will be made by the investigator conducting the consent discussion in consultation with the research team as needed. Parents will be given the opportunity to ask questions. Once all questions have been answered, parent(s) will be asked to sign and date the consent form. Parents will be provided with a copy of the signed consent form.

Child Assent The children in this study (ages 5 to 12 yrs 11 months) will be diagnosed with ASD and repetitive SIB. Some will also be cognitively delayed. The PI or designated Co-investigator conducting the consent procedure will evaluate the child's capacity to provide written or verbal assent. The investigator's judgment will be documented on the assent form.

Consent for Video Recording Consent for video recording for research purposes will be obtained from parents. If parents are willing, video recordings will be used for training purposes (e.g., presentations at professional meetings). Parents can indicate agreement or disagreement with this additional use of the videos directly on the video consent form. Agreement to use the videos for these additional training purposes is not required for study participation.

Study Withdrawal Parents are free to withdraw from the study at any time. This will be clearly stated during the consent process. Subjects may need to discontinue participation in the study before completion for various reasons (e.g., family move, withdrawal of consent, adverse events, need for a different treatment). Parents who indicate intention to withdraw the child from the study will be offered to have a case conference with the study team to discuss the matter. If the discussion indicates that the child needs another treatment, we will assist the family to locate that treatment. Parents who drop out of treatment will be invited to return for scheduled assessments or an early termination visit. Data collected from children who drop out of treatment, but return for assessments, will be analyzed in their originally randomized group.

Confidentiality

Case report forms (CRFs) contain the subject's unique ID number – but no identifying information. DEX is a secure, password protected data base. The folders containing CRFs data will be kept in locked files and access to these files is only granted to members of the research team. Standardized tests (e.g. IQ and language tests) record the child's date of birth in order to calculate the child's age for comparison to normative data. No other personal health information will be documented on research forms. Contact information for the family is kept in a separate file that is in a locked cabinet.

Certain measures will be recorded on video. The digital files are stored on a secure, password-protected site. Recordings may also be stored electronically on an encrypted external hard drive that is kept in a locked closet or cabinet. The digital files will be marked with a Subject ID instead of names of children or their parents. It is possible that names may be mentioned on the recordings. Video recordings from this research study will be retained for up to 5 years after the study is over. Recordings may be used for other purposes (e.g. presentations at professional meetings) if separate consent is obtained from the parent (or guardian).

Access to study records (case report forms) will be restricted to study staff. Others that have access to the record include individuals with regulatory responsibility at Emory, Children's Health Care of Atlanta (CHOA). All clinical trials are subject to routine audits by offices at Emory or CHOA.

Potential Benefits of the Proposed Research to the Subjects and Others

Subjects may directly benefit by the receipt of NAC. Subjects initially randomized to placebo will be offered treatment with NAC in the 9-week, open-label extension trial. Overall, the risks to the subjects in this research are similar to those that exist in standard clinical practice and the proposed research project offers the potential for improving treatment of

moderate repetitive behavior in children with ASD. Indeed, this research may lead to a new treatment option for repetitive behavior in children with ASD. Thus, the potential benefits of the research outweigh the risks involved.

Importance of the Knowledge To Be Gained Children with ASD with language delay are impaired and, untreated, their long-term prognosis is guarded. Although current treatments are helpful in some cases, significant gaps in our treatment options remain. There are no large, controlled clinical trials of NAC in children with ASD and no medication treatments for the core feature of repetitive behavior in children with ASD. This study may provide new information about the treatment of repetitive behavior in children with ASD and may identify subgroups of affected children who could benefit from this treatment.

Data Safety and Monitoring Plan

This pilot study will not have an external Data and Safety Monitoring Board. It will be conducted in accordance with “good clinical practice” as outlined in the International Conference on Harmonization of Technical Requirements for Registration of Pharmaceuticals for Human Use (Dixon & Hallinan, 1999).

The Steering Committee will be comprised of the PI, Drs. [name], [name] and [name], [name] and the data manager from DEX. Drs. [name] and [name] and the data manager will meet at least once a month to discuss the conduct of the trial including recruitment, attrition, attendance and rate of successful data collection. Problems or concerns identified will be reviewed with the Steering Committee will provide oversight and ensure that the study is conducted in accordance with the protocol.

The unblinded data manager (member of the DEX team) will serve as an independent monitor of data quality and safety with input from [name] as needed. The data manager will have direct access to the study data base in DEX and will conduct regular checks on recruitment, attendance, missing data, attrition and adverse events. [name] will provide a summary every six months for [name] review of these same metrics (recruitment, attendance, missing data, attrition and adverse events). Questions and concerns will be brought to the Steering Committee as needed. To protect the blind, treatment assignment will not be divulged. The discussion with the Steering Committee is likely to focus on individual cases and overall trends. Given the sample size of 14 (7 per group) in this pilot study, we have not declared any **stopping rules** for benefit or futility. In the unlikely occurrence of a serious adverse event, [name] will confer with [name] (Medical Director at Marcus) to judge whether the event is an SAE and whether it is possibly, probably or definitely related to the study drug (see below for reporting SAEs). This review of potential SAEs will include deliberation on whether to break the treatment blind for the participant. In each situation, we will presume that the participant is on the active medication and consider the possible medical implications – given that assumption. The blind will be broken only if medically indicated by the PI and [name]. The treatment assignment will not be disclosed to the treating clinician, independent evaluator, coordinator, or behavior data analysts.

Monitoring for Adverse Events (AEs):

At each visit, including baseline and interim contacts, the treating clinician will systematically review for adverse effects and concomitant medications using an Adverse Effects Review form developed for this study. We have used versions of this form, in several multi-site clinical trials in children with autism (RUPP Autism Network, 2002; Autism Network, 2005b; [name] et al., 2006; Aman et al., 2009; [name] et al., 2015). It contains a general inquiry, drug-specific queries, and several questions about daily activities (e.g., sleep, appetite, energy level, bowel and bladder functions). The general inquiry includes an open-ended question about any problems or complaints, as well as questions regarding the need for other medications and doctor or health care encounters since the last study visit. The next section includes drug-specific queries, probing for adverse events that have been reported in the scientific literature. These items are rated as not present, mild, moderate or severe. The ratings: mild, moderate or severe are defined as follows: mild= present, but no intervention required; moderate=present, may be bothersome or may require intervention; severe=present, bothersome and requires intervention. The last section includes specific questions about daily activities. All **new** adverse events (mild, moderate or severe) will be documented on the adverse event log. The status of previously-reported adverse events will be monitored as well. In the prior RUPP Autism Network studies, the form was easily modified to

make it relevant for risperidone (RUPP Autism Network, 2002), methylphenidate (RUPP Autism Network, 2005b) and guanfacine ([name] et al., 2015). We will include queries about self-harm or expressions of suicidal thoughts or plan.

When the treating clinician elicits an adverse event (AE), it will be documented regardless of suspected relationship to the study drug. The adverse event log requires the treating clinician to label the AE (using a list of preferred terms and a numeric code) and to document the severity, onset, course, outcome, and attribution (study drug related or not).

Attribution is classified as follows:

- Definite: AE is clearly related to the study drug.
- Probable: AE is likely to be related to the study drug.
- Possible: AE may be related to the study drug.
- Unlikely: AE is doubtfully related to the study drug.
- Unrelated: AE is clearly not related to the study drug.

Severity of AEs is classified as follows:

- Grade 1 mild = present, clinical observation only, intervention not indicated;
- Grade 2 moderate = present, minimal, local or noninvasive intervention indicated; may limit age-appropriate instrumental activities of daily living;
- Grade 3 severe = present, medically significant but not immediately life-threatening; may not need hospitalization or may not prolong current of hospitalization indicated; potentially disabling; likely to limit self-care activities of daily living.

NOTE: if hospitalization is required – prepare Serious Adverse Event report (see below).

- Grade 4 Life-threatening (serious adverse event) = urgent intervention indicated.
- Grade 5 = Death.

During the study, participant with Grade 3 or 4 AE should receive appropriate treatment and may have to stop study drug. Decisions on the appropriate care of the subject will be made by the treating clinician, the PI, the research study team (all of whom will remain blind to study treatment). The treatment plan will be set up in collaboration with the child's primary care provider whenever possible. Depending on the nature of the Grade 3 or 4 AE, the research team, in consultation with the family, may recommend unscheduled medical testing. Abnormal findings on laboratory tests will be investigated to inform the treatment plan. If the abnormality fails to normalize after stopping study drug, the subject should be referred and followed until resolution of symptoms.

Routine reporting of AEs Adverse events will be documented on the Adverse Event Log as described above. All AE data will be captured in the electronic database and reviewed by Drs. [name] and [name] on a regular basis, at least quarterly. AEs occurring at a greater than expected frequency or severity will be reviewed with the Steering Committee.

Investigators will provide this information to the Emory IRB based on IRB Policy & Procedures (P&Ps). The Steering Committee will decide if modifications to the protocol or consent form are required.

AEs resulting in treatment discontinuation: Adverse events that are the primary reason for study discontinuation will be tracked separately. The data manager will provide a table with all such side effects to the PI three times a year.

Serious adverse events: A serious adverse event (SAE) is defined as an event that poses a threat to the participant's life or functioning. We note that "severe" is not necessarily equivalent to "serious." Thus, a severe rash may not be a serious adverse event, whereas a heart attack of any severity is likely to be a serious adverse event. A serious adverse event is defined as any event that entails one of the following:

- Death;
- Threat to the individual's life;
- Inpatient hospitalization or prolongation of existing hospitalization;
- Persistent or significant disability or incapacity;
- Intentional drug overdose;
- Any other significant event that jeopardizes the participant.

Assessment and Reporting of Serious Adverse Events If an adverse event meets the definition of an SAE, the PI in consultation with [name] will determine whether the SAE is possibly, probably or definitely related to the study drug.

The PI will report SAEs to the local IRB as required by IRB P&Ps (within 10 business days) under the following circumstances: a) serious AND unanticipated AND possibly, probably or definitely related events; and b) anticipated adverse events occurring with a greater frequency than expected. SAEs that do not meet any of these circumstances will be reported with IRB re-approvals. Written IND safety reports will be submitted to the FDA by the IND sponsor, [name], for serious, unexpected suspected adverse reactions within 15 calendar days of learning of its occurrence. If the event is fatal or is deemed to be life threatening, the report will be made within 7 calendar days. The IND sponsor will also make an assessment of whether the event constitutes an unanticipated problem (UP) posing risks to subjects or others. This assessment will be provided to the Emory University IRB, which, in turn will make a final determination. If the Emory IRB determines an event is a UP, it will notify the appropriate regulatory agencies and institutional officials.

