Improvement item on the Clinical Global Impression scale (CGI-I) The CGI-I is a 7-point scale designed to measure overall improvement from baseline ([name] et al., 2015). Scores range from 1 (Very Much Improved) to 4 (Unchanged) to 7 (Very Much Worse). The CGI-I will be used to assess overall response to treatment. By convention, scores of Much Improved or Very Much Improved are used to define *positive response*; all other scores are classified as a *negative response*. Using available information (ABC scales, Parent Target Problems, Parent Daily Rating), the CGI-I will be rated by a blinded independent evaluator ([name]) trained by [name].

Aim #4 [Safety and Tolerance]

A blood sample for routine lab tests (CBC, BUN, creatinine, liver function panel) will be collected at screening and at endpoint. These lab results will be reviewed by [name] (Pediatric Nurse Practitioner) with consultation from Drs. [name] and [name] as needed. Clinically important findings will be shared with the family.

Adverse Events At each visit the treating clinician will ask specific queries about major body systems, activity level, sleep, appetite, and general health. The assessment will be guided by the Adverse Events Review. This measure will be conducted at baseline so that current health complaints are known and documented. New events, whether presumed related to treatment or not, are classified as an adverse event and rated as Mild, Moderate or Severe (See Appendix B for definitions).

Aim #5 [Biomarkers and Mechanism of Action]

In addition to the blood drawn for safety monitoring, we collect an additional tube (2 cc, lavender top) of whole blood to examine redox couples and amino acid neuromediator levels before and after NAC treatment. Samples will be centrifuged twice to obtain platelet-free plasma. These samples will be analyzed in [name] lab using ultra-sensitive, quantitative mass spectrometry methods (Tirouvanziam et al., 2006; Tirouvanziam et al., 2012; Hardan et al., 2012; Conrad et al., 2015). NAC has been shown to affect cysteine/cystine and glutathione/glutathione disulfide (GSH/GSSG) redox couples in blood, as well as levels of glutamate, glutamine and possibly, GABA. Measurement of these indices may inform the possible mechanisms of action of oral NAC (e.g., rebalancing key redox metabolites and/or excitatory/inhibitory amino acids) that may be relevant in the treatment of SIB in children with ASD.

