Aim #4: Adverse events (AE) will be systematically monitored using a 34-item Adverse Events Review form that was developed by the RUPP Autism Network to assist with the elicitation and assessment of adverse effects. It includes specific queries about major body systems, activity level, sleep, appetite, and general health. New events, whether presumed related to treatment or not, are classified as AEs and rated as Mild, Moderate, or Severe (see Appendix B). The occurrence of an AE will be counted once at the highest level of severity (e.g., a report of mild nausea followed by a report of moderate nausea in the same child would be counted as an occurrence of moderate nausea). Given the small sample size, it is unlikely that any AE will be significantly more common in NAC compared to placebo. Nonetheless, we will evaluate the frequency of AEs across groups using a Fisher's exact test (classification and reporting of AEs is described in Appendix B).

Change in direct observation measures from baseline to Week 9 will be evaluated using paired t-tests within the treatment groups and ANCOVAs across groups as previously described. Secondary measures will be assessed using longitudinal linear regression models and consider change in measure scores both within and across study groups over time.

Aim #5: Aim #5. To evaluate biomarkers and possible mechanisms of action of NAC in children with ASD.

Given the sample size, we do not expect to observe differences between groups. Using mass spectrometry, we expect increased cysteine/cystine and glutathione/glutathione disulfide (GSH/GSSG) ratios, and decreased glutamate/glutamine ratio and increased GABA levels in the NAC-treated group. These assays will use < 2 ml of blood collected at screening and endpoint when blood samples for safety are also being collected.

References

Alvarez, J. P., [name], N. A., Lomas Mevers, J. E. (2014). Increasing the Social Validity of Function-Based Treatments for Problem Behavior. *Acta de Investigación Psicológica*, 1673-1682.

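### Do the two wordings of mild, moderate and severe in Appendix B leave the Aim 4 severity count undefined?

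*Combined protocol and SAP*

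**What the plan says.** The Aim #4 paragraph under Data Analysis says that new events "are classified as AEs and rated as Mild, Moderate, or Severe (see Appendix B"). Each AE is then counted once per child, at its worst recorded level, and AE frequency is compared between groups with Fisher's exact test. The Aim #4 [Safety and Tolerance] section and the Adverse Events Review entry in Appendix A use nearly the same pointer: "rated as Mild, Moderate or Severe (See Appendix B for definitions").

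Appendix B, under Monitoring for Adverse Events, words the levels in two places.

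- **Review form.** After describing the form's drug-specific queries, it says: "These items are rated as not present, mild, moderate or severe". Mild is an event that needs no intervention. The next two levels are "moderate=present, may be bothersome or may require intervention; severe=present, bothersome and requires intervention".
- **AE log.** When the clinician elicits an AE, the log requires the clinician "to document the severity, onset, course, outcome, and attribution". Two parallel lists follow. The first classifies attribution. The second opens "Severity of AEs is classified as follows" and runs from Grade 1 to Grade 5. Its first two entries are "Grade 1 mild = present, clinical observation only, intervention not indicated" and "Grade 2 moderate = present, minimal, local or noninvasive intervention indicated; may limit age-appropriate instrumental activities of daily living". Grade 3, severe, turns on medical significance. Grades 4 and 5 are life-threatening events and death.

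**The concern.** The pointers send the reader to Appendix B for one set of definitions, and the reader finds two built on different criteria. Bothersomeness appears only in the form wording. Medical significance and limits on daily activities appear only in the graded list. Within the form wording, moderate and severe also overlap: an event that bothers the child and needs intervention satisfies both.

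Safety and tolerability is a stated aim, and severity is part of its counting rule. If the wordings can place the same event at different levels, the Aim 4 severity table could depend on which one the clinician had in mind. The Steering Committee's review of AEs of greater than expected severity draws on the same ratings.

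**Working it through.** The plan gives no figure to reproduce. The check compares the two texts and then sizes the largest shift they allow.

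**1. What each wording is attached to.** The form wording is stated for checklist items and includes a not-present level, which an item can have and a recorded AE cannot. The graded list is stated for AEs and follows the sentence that makes severity a log field, next to a matching list for attribution, another field in that sentence. Aim 4 counts occurrences of AEs, not form items.

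**2. What surrounds the graded list.** The paragraph on handling Grade 3 or 4 events works only if AEs carry a Grade. The Routine reporting of AEs paragraph refers back to the log as already described and says that AE data go into the database. The Aim #4 analysis paragraph refers to Appendix B for the classification and reporting of AEs. All three point to the graded list.

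**3. Where the wordings can part.** Take events with no limit on daily activities and no medical significance (an assumption made to keep the comparison simple). Cross bothersome (no/yes) with intervention (none/minimal):

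| Event profile | Levels that fit the form wording | Graded list |
|---|---|---|
| Not bothersome, no intervention | mild | Grade 1 mild |
| Not bothersome, minimal intervention | moderate | Grade 2 moderate |
| Bothersome, no intervention | mild or moderate | Grade 1 mild |
| Bothersome, minimal intervention | moderate or severe | Grade 2 moderate |

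The level can differ in 2 of 4 profiles, by one step at most. It must differ in 0 of 4, because in every row the graded level is among those that the form wording allows. The third row is the weaker case, since such an event meets the form's definition of mild outright.

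**4. Size.** The Data Safety and Monitoring Plan gives 14 children, 7 per group. Suppose one child in an arm has nausea of the fourth profile:

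- Graded list: moderate 1/7 = 14.3%, severe 0/7 = 0%.
- Form wording, if read as severe: moderate 0/7 = 0%, severe 1/7 = 14.3%.
- Nausea at any level: 1/7 = 14.3% on both.

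The 14.3 points reflect the arm size for one assumed child. The documents give no rate for such events.

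**5. What depends on the label.** The planned Fisher's exact test is on AE frequency, so it takes the any-level count, which does not move. Serious adverse events have their own criteria. The Grade 3 or 4 paragraph uses Grades by name. The treating clinician who rates AEs is blinded, so nothing here favours one arm. Only the split by level in a descriptive table and the severity part of the Steering Committee's review are left.

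**The case for a change.** The strongest case for a change is that the text never says the Grades govern. Appendix B sends new AEs to the log as mild, moderate or severe before any Grade is mentioned. The Aim 4 and Appendix A pointers use three levels, as the form does, while the list has five. Two of those pointers describe the review form and promise definitions, which echoes the way the form wording is introduced. The plan's own example, nausea, is listed in the Specific Aims among the common adverse effects of N-acetylcysteine. It is therefore probably one of the drug-specific items rated on the form before it reaches the log, although the item list is not shown. No rule turns a form rating into a log grade.

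Part of this stands: there is no express sentence, and the overlap of moderate and severe on the form is real. The rest does not decide the matter. Grades 1 to 3 carry the same three names, so the three-level wording fits either reading. The subject of the pointers is new events classified as AEs, which suits the list for AEs at least as well as the list for form items.

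One could add that, if AEs were tested by severity level, moving one child might matter: with 7 per arm, two-sided Fisher p-values are 0.070 for 4 v 0 and 0.021 for 5 v 0. The plan states no such test, so this carries no weight.

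**Conclusion.** No change to the plan is needed. Appendix B has a form-item rating and an AE severity scale, and the order of the text makes the second the natural one for logged AEs and for the Aim 4 count. This is an unstated cross-reference, not an internal contradiction, because both wordings can be applied to every profile examined without disagreement. At worst, one child's event moves one level in a descriptive table, 14.3 percentage points in an arm of 7. The number of children with the event, the between-group test, serious-event reporting and Aim 4's conclusion on how often events occur are untouched.

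This rests on two readings: that the log's severity field uses the list that follows it, and that Fisher's test counts AEs whatever their level. Both follow from the layout and wording of the plan. Nothing here judges which definition is clinically preferable. A sentence naming the scale would do no harm, but it would only record what a sensible analyst would do anyway.
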